A Randomized Control Trial Investigating the impact of High dose Prophylactic Tranexamic acid on blood loss at the time of minimally invasive myomectomy – Protocol

Proposed Research Study:

A Randomized Control Trial Investigating the impact of High dose Prophylactic Tranexamic acid on blood loss at the time of minimally invasive myomectomy

Investigators:

[name] [name] MD [name] [name] MD [name], PhD [name] [name] MD

Specific aim:

- 1. To compare the volume of blood loss in patients undergoing minimal invasive myomectomies who received prophylactic tranexamic acid vs placebo
- 2. To compare the number of blood products received during/post procedure in patients received tranexamic acid prophylactically vs placebo

This will be conducted as a double blinded randomized control trial. Data will be collected over a 3 year period with the goal of recruiting 50 patients per arm

Background and Significance

In minimal invasive gynecologic surgeries, operative blood loss is a common complication that affects postoperative morbidity and recovery (1). Antifibrinolytic drugs are well established in the management of surgical and traumatic bleeding(1–3). Tranexamic acid (TXA) is a synthetic lysine derivative that binds to plasminogen and inhibits the enzyme from breaking down fibrin deposits. In a recent Cochrane review last updated in 2015 that investigated the use of TXA in general surgery, TXA was found to reduce intraoperative and postoperative blood loss by 414 mL (95% confidence interval [CI] –525 to –303 mL) in comparison to placebo(4). In another Cochrane review 16 trials involving benign obstetrics and gynecologic were included. 14 studies involved women undergoing elective Cesarean deliveries and 2 studies involved women having abdominal myomectomy. No studies involving hysterectomy were identified and no studies involving minimal invasive myomectomies were identified(1)(5). Only recently, the first Randomized controlled double blind study was completed at George Washington University (6).

The results of this study have yet to be published. We hope to attempt to show the efficacy of prophylactic TXA use in minimal invasive myomectomies in reducing blood loss.

Study Design

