Both surgeon and patient will be blinded to the treatment arm. This dosage has been used previously in both obstetric and gynecological procedures and is the same dose recommended by the WHO for preventing post-partum hemorrhage(13).

The surgery itself will be scheduled at either Sentara Norfolk General, Sentara Leigh hospital, and Sentara Princess Anne hospital. These are the three sites that the investigators already perform Minimally invasive myomectomies.

An envelope will be given to the anesthesiologist prior to the procedure informing whether they are to receives TXA or the placebo. Blood loss will be estimated by the surgeon performing the procedure. Hemoglobin and hematocrit will be obtained 24 hours post procedure. The patient will be assessed for reported side effects from the medication given will be assessed by a questionnaire that will be given at their post-op appointment at the 2 week and 6-week mark. During these two visits a physical exam is performed, checking incision sites, and patient symptoms, all of which are standard of care for any minimally invasive procedure. The patients will be seen at the EVMS outpatient clinic for Gynecology or

depending with the physician who performed the surgery. Data will be collected from both Allscripts and EPIC charts.

Primary Outcomes measured

- 1. Estimated blood loss at time of procedure completion; using volume of cannister and weight of lap sponges
- 2. Calculated Blood loss, using pre-operative hematocrit, postoperative hematocrit and estimated blood volume x Body Mass Index
- 3. Number of blood products received during admission that is directly due to blood loss at time of procedure

Secondary outcomes

- 1. Duration of surgery
- 2. Length of hospital stay
- 3. Number of fibroids removed
- 4. Fibroid types 0-8
- 5. Total Weight of fibroids removed
- 6. Pain index on post-operative day 1, and 2-week post-operative visit
- 7. Post-operative complications
 - a. Readmission
 - b. Postoperative fever
 - c. Postoperative infection
- 8. Reported mild side effects of medication (Supplement 2)
 - a. Diarrhea
 - b. Nausea
 - c. Headache
- 9. Reported Serious Side effects of medication (Supplement 2)
 - a. Shortness of breath
 - b. Deep vein thrombosis
 - c. Pulmonary Embolism

Patient data will be collected in a data collection tool with the subjects de-identified.

A subject identifying tool will also be sued to identify the subject with their EPIC and Allscripts MRN.

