Both epic and Allscripts will be used to collect patient data

Inclusion Criteria

- 1. Female
- 2. Age 18-45

- 3. Undergoing laparoscopic myomectomy
- 4. At least one fibroid greater than or equal to 6 cm
- 5. Any intramural or broad ligament fibroid greater than or equal to 4 cm
- 6. At least 3 total fibroids based on preoperative imaging

Exclusion Criteria

- 1. Severe existing medical complications involving the heart, liver, or kidney
- 2. Moderate to severe renal impairment (serum creatinine > 1.4)
- 3. Blood clotting abnormalities
- 4. Age <18
- 5. Known Allergies to tranexamic acid
- 6. Known Contraindications to Minimally invasive myomectomies
- 7. If you are pregnant
- 8. History of a prior blood clot in the lung, arm, or leg, known as pulmonary embolism or deep vein thrombosis
- 9. Any active blood clots, clotting disease, pulmonary embolism, cerebral thrombosis, estrogen use, renal impairment, elevated creatinine level
- 10. History of a stroke or mini-strokes

11. History of prior seizures

- 12. Concurrent oral contraceptive use
- 13. Contraindications to receiving Tranexamic acid
 - i. In patients with acquired defective color vision, since this prohibits measuring one endpoint that should be followed as a measure of toxicity
 - ii. In patients with subarachnoid hemorrhage. Anecdotal experience indicates that cerebral edema and cerebral infarction may be caused by tranexamic acid in such patients.
 - iii. In patients with active intravascular clotting.
 - iv. In patients with hypersensitivity to tranexamic acid or any of the ingredients

Statistical Analysis

Descriptive statistics will be calculated. Continuous variables will be compared with t-test and categorical variables will be compared with Chi-square. P-values of less than 0.05 will be considered significant. A logistic regression will be performed to calculated the adjusted odds ratio.

Sample size calculation was set at 90 % power to detect a 150 ml difference in blood loss, with a significant level of 5 % and a one-sided alpha of 0.05 and beta (β)-set at 0.1.

The sample size was calculated using the formula below.

N=2 Σ^{2} (z α +Z1/2 β)²/r²

Substituting with figures:

 $N=2\times135\times135(1.96+1.282)^2/150^2=17$ patients in each group.(14) However, we wish to include 50 patients on each arm to try to increase the chances of identifying any side effects associated with the procedure

Risks of Study

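### Calculated blood loss (primary outcome 2) has no term for transfused red cells, so women given red cells before the 24-hour hematocrit are scored too low, and the arm difference shrinks to the extent that placebo patients receive more of them

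*Combined protocol and SAP*

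**What the plan says.** Under Primary Outcomes measured, item 2 is "Calculated Blood loss, using pre-operative hematocrit, postoperative hematocrit and estimated blood volume x Body Mass Index". These are ingredients; no equation is given. Study Design fixes the second sample: "Hemoglobin and hematocrit will be obtained 24 hours post procedure". No other postoperative hematocrit is mentioned, and nothing says how a transfused woman is to be handled.

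Transfusion is recorded separately. Item 3 of the same list is "Number of blood products received during admission that is directly due to blood loss at time of procedure", and the second specific aim is "To compare the number of blood products received during/post procedure in patients received tranexamic acid prophylactically vs placebo". Neither is linked to item 2. Under Statistical Analysis, "Continuous variables will be compared with t-test", with no adjustment for transfusion. The design difference is given there too: "Sample size calculation was set at 90 % power to detect a 150 ml difference in blood loss".

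**The concern.** A hematocrit-based loss is a red-cell balance: the fall between two samples is converted into a volume of blood. Red cells infused between the samples make the fall smaller. With no term for them, the calculation understates the loss in exactly the women who bled enough to be transfused. A transfused heavy bleeder can rank below an untransfused woman who lost far less.

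Transfusion happens after randomization and may be affected by treatment. If placebo patients receive more red cells before the draw, their mean loss is understated more, and the estimated benefit of tranexamic acid on this outcome moves toward zero. Outcomes 2 and 3 would then pull against each other. Deciding how to score transfused women after seeing the data would also leave room for a post hoc choice on a primary outcome.

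**Working it through.** **The plan's own figure.** Statistical Analysis gives SD 135 mL, difference 150 mL and z-values 1.96 and 1.282: 2 × 135² × (1.96 + 1.282)² / 150² = 17.03, which reproduces the stated 17 per group. (The text describes "with a significant level of 5 % and a one-sided alpha of 0.05 and beta (β)-set at 0.1", but 1.96 is the two-sided value; 1.645 would give 13.9.) Planned enrolment is 50 per arm.

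**Assumptions not in the documents.** Blood volume V, pre-operative hematocrit H0 and red cells per unit must be assumed. After an isovolemic loss L, the hematocrit is H1 = H0 × exp(−L/V). Loss is scored as V × (H0 − H1) / mean(H0, H1), a common form, because the plan gives no equation.

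**One patient.** V = 4,550 mL (70 kg × 65 mL/kg), H0 = 0.36, each unit raising hematocrit by 0.03 (0.03 × 4,550 = 136.5 mL of red cells).

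| True loss | Units before draw | 24-hour hematocrit | Scored loss |
|---|---|---|---|
| 400 mL | 0 | 0.330 | 400 mL |
| 1,000 mL | 0 | 0.289 | 996 mL |
| 1,000 mL | 1 | 0.319 | 550 mL |
| 1,000 mL | 2 | 0.349 | 142 mL |

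The woman who lost 1,000 mL and had two units is scored below the one who lost 400 mL.

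**Loss hidden per unit.**
- Dividing by H0 alone: 0.03 × 4,550 / 0.36 = 379 mL at three points per unit. At 180 mL per unit, 180/0.38 = 474 mL to 180/0.33 = 545 mL.
- Mean-hematocrit form, 1,000 mL loss, one 180 mL unit: with V = 5,000 and H0 = 0.38 the score falls from 997 to 452 mL (545 hidden). With V = 4,000 and H0 = 0.33 it falls from 995 to 354 mL (641 hidden).

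So 400-600 mL is a round working range. The mean-hematocrit form can exceed it when loss is heavy.

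**Trial level.** Measured difference ≈ 150 − (arm difference in mean units per patient before the draw) × (400 to 600 mL).

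| Difference in mean units | Shrinkage | Measured difference | Power, n = 50, SD 135 |
|---|---|---|---|
| 0 | 0 | 150 mL | >99.9% |
| 0.05 | 20-30 mL | 120-130 mL | >99% |
| 0.10 | 40-60 mL | 90-110 mL | about 91-98% |

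**Simulation** (skewed loss, transfusion modeled by a hematocrit cut-off purely as a computing device). With SD 135 mL, a true difference of 150 mL and assumed placebo means of 300-400 mL, 0-1% of women were transfused and shrinkage was 0-5 mL. With mean 700 and SD 500 mL, placebo transfusion was 2-13% and a true 150 mL difference was measured as 99-147 mL.

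**Checking the correction** (1,000 mL, two units of 136.5 mL, total 273 mL).
- Adding 273 / mean hematocrit to the uncorrected score: 142 + 273/0.354 ≈ 912 mL. This falls short because the mean has already been raised by the transfusion.
- Correcting the hematocrit first: 0.349 − 273/4,550 = 0.349 − 0.060 = 0.289, which scores 996 mL, the same as with no transfusion.

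**The case against.** The strongest reply is that the effect may be negligible here. The documents give no transfusion rate, timing or transfusion rule. Shrinkage needs red cells, given before the draw, and more of them on placebo. At the plan's own SD of 135 mL, losses of 1,000 mL are very rare, and simulated shrinkage is at most 5 mL. Larger values appear only under a heavier, skewed distribution that the documents do not describe. This stands, and it rules out any firm trial-level figure.

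A reader might infer that any benefit of tranexamic acid is necessarily shrunk. The documents do not support that. The second aim is only to compare blood products, and the Study Design remark on transfusion need sets high against regular dosing in other specialties. A reader might also multiply a 12-point difference in transfusion rate by 2 units and 600 mL to get 144 mL, nearly the whole design difference. None of those inputs is in the plan, and all are at their upper end. Item 3 counts products over the whole admission, and units given after the draw cannot affect that hematocrit.

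Nor does a loss of power follow. Compressing the upper tail lowers the SD, and in several simulated settings power rose while the estimate was biased (for example 0.40 uncorrected against 0.31 corrected).

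Finally, item 2 lists ingredients, so a transfusion term might be intended. But none is listed, and following the list as written gives a wrong value for each woman transfused with red cells before the draw. That does not depend on the balance between arms.

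**Conclusion.** The concern holds in conditional form. As written, primary outcome 2 understates loss by roughly 400-600 mL per red-cell unit given before the 24-hour sample, assuming a blood volume of 4,000-5,000 mL, pre-operative hematocrit 0.33-0.38 and 180 mL of red cells per unit. The arm difference is biased toward zero only to the extent that placebo patients receive more red cells before the draw. That size cannot be determined from the documents: near zero if transfusion is rare or balanced, and about 20-60 mL for a difference of 0.05-0.10 units per patient. Primary outcome 1, from canister volume and sponge weight, does not use hematocrit and is untouched. This is a defect in one of three primary outcomes that should be fixed, not a threat to the whole trial.

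**What to change.** State the complete formula for primary outcome 2, including a blood volume in mL; the product with body mass index is undefined and needs resolving in the same edit. Then define:

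corrected postoperative hematocrit = 24-hour hematocrit − (red-cell volume transfused between the two samples / estimated blood volume)

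Use the corrected value in both the difference and the mean hematocrit. Count all red-cell units and any salvaged red cells given between the samples, whatever the reason. The item 3 count cannot serve: it covers all blood products, the whole admission, and only those attributed to procedural bleeding. Fix a standard red-cell volume per unit in advance, and report the uncorrected value as a sensitivity analysis.

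The cost is a few sentences and some chart fields: product type, time of each unit, salvaged volume and time of the draw. The charts are already the data source. The downside is the assumed volume per unit. In the 1,000 mL, two-unit example, if units truly held 200 mL but 180 mL were assumed, the corrected hematocrit would be 0.289 + (400 − 360)/4,550 = 0.298 and the score about 861 mL. That is still far closer than the uncorrected score, which would be below zero (4,550 × (0.360 − 0.377)/0.368 ≈ −210 mL).

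### Side effects are the stated reason for 50 per arm, yet the only stated comparison for secondary outcomes 7–9 is chi-square at p<0.05, with no interval, which says little about uncommon harms

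*Combined protocol and SAP*

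**What the plan says.** The sample size paragraph under Statistical Analysis is about blood loss: "Sample size calculation was set at 90 % power to detect a 150 ml difference in blood loss". It arrives at 17 per group and then gives one reason for going further: "However, we wish to include 50 patients on each arm to try to increase the chances of identifying any side effects associated with the procedure".

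Under Secondary outcomes, item 7 lists readmission, fever and infection. Item 8 lists diarrhea, nausea and headache. Item 9, "Reported Serious Side effects of medication (Supplement 2"), lists shortness of breath, deep vein thrombosis and pulmonary embolism.

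The analysis text that reaches these outcomes is short. "Descriptive statistics will be calculated", with no detail. For comparisons, "categorical variables will be compared with Chi-square. P-values of less than 0.05 will be considered significant". Finally, "A logistic regression will be performed to calculated the adjusted odds ratio", with neither outcome nor covariates named.

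The plan does not state an interval for any event rate or difference, the version of chi-square, a rule for sparse tables, a harm rate to be detected, or how a non-significant safety result will be read.

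**The concern.** Two thirds of the enrolment (100 − 34 = 66 women) is justified by side effects, but no analysis is fitted to that purpose. A p-value threshold suits a question for which the trial was sized. For uncommon events at 50 per arm it will usually return a non-significant result whether or not a moderate harm exists, and without an interval the reader cannot see how much harm remains possible.

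The rule is also incomplete. At small counts the uncorrected, continuity-corrected and exact versions can fall on opposite sides of 0.05, so the reported verdict may depend on a software default. What is at stake is what the trial can say about harm. The blood-loss analysis is not affected.

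**Working it through.** **Inputs from the protocol.** SD 135 ml, difference 150 ml, z values 1.96 and 1.282, 50 per arm, chi-square at p<0.05 (all Statistical Analysis).

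**Inputs assumed.** All event rates. Risks of Study gives only bands for prolonged use (above 10%, which includes headache, and 1% to 10%). There is no placebo rate, no target difference, and no figure for thrombosis, fever, infection or readmission. A range is therefore shown.

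**1. The plan's own figure.** N = 2 × 135² × (1.96 + 1.282)² / 150² = 17.03, printed as 17. It reproduces. No corresponding figure is given for side effects.

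**2. Power at 50 per arm.** For each pair of rates, the binomial probabilities of all 51 × 51 possible tables are summed over those with two-sided p<0.05.

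| Assumed rates | Uncorrected chi-square | Fisher |
|---|---|---|
| 1% v 4% | 8.6% | 0.9% |
| 2% v 4% | 5.4% | 0.6% |
| 5% v 10% | 14.5% | 6.3% |
| 10% v 20% | 30% | 19.5% |
| 5% v 20% | 66% | 51% |
| 10% v 30% | 73% | 64% |

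The continuity-corrected test matches Fisher to the digits shown. For 80% power, 5% v 10% would need 435 per arm and 2% v 4% would need 1141.

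**3. Dependence on the version of the test.** With equal arms, the expected number of events per arm is half the total, so it is below 5 whenever there are fewer than 10 events in all. For 4 v 0:

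- Pearson: χ² = 100 × (4 × 50 − 0 × 46)² / (4 × 96 × 50 × 50) = 4.17, p = 0.041.
- Fisher: 2 × C(50,4) / C(100,4) = 0.117.

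Other splits, Pearson v Fisher: 5 v 0, 0.022 v 0.056; 7 v 1, 0.027 v 0.059; 8 v 2, 0.046 v 0.092. The chance of a table on which the two disagree is 4.9% at 2% v 4%, 7.7% at 1% v 4%, 19% at 2% v 10% and 24% at 1% v 8%.

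**4. False positives.** With equal rates in both arms, the exact size of the uncorrected test is 0.2% at a 1% rate and about 5.5% at 15%. Inflation is not the problem.

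**5. What an interval would show.** The exact two-sided 95% upper limit for 0/50 is 1 − 0.025^(1/50) = 7.1%; for 1/50 it is 10.6%. With no events in either arm, the Newcombe 95% interval for the difference is −7.1 to +7.1 percentage points. With 2 v 0 the difference is 4 points (−3.7 to 13.5), where the plan's rule would report only p = 0.15.

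**The case against.** Several objections carry weight.

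- **The aim is to see events, and it is partly met.** The wording is hedged and concerns identifying side effects; it does not claim a powered comparison. At an assumed 2% rate, the chance of at least one event in the treated arm is 1 − 0.98¹⁷ = 29% with 17 women and 1 − 0.98⁵⁰ = 64% with 50. A reader might infer that the larger sample fails its purpose altogether. It does not. But this supports reporting counts with intervals more than it supports a p<0.05 rule.
- **Chi-square is not the only thing planned.** Descriptive statistics would ordinarily give counts per arm, a logistic regression is mentioned, and Risks of Study sends serious adverse events to FDA MedWatch and the IRB without any test. That stands. Still, none of these is specified so as to give a safety interval, and an ordinary maximum-likelihood odds ratio has no finite estimate when one arm has no events.
- **Much of the disagreement is Fisher's conservatism.** This is correct. The uncorrected test holds its size reasonably well, and Boschloo's exact test sides with it at 5 v 0, though not at 4 v 0. The defect is that the version is left open. The uncorrected test is not invalid.
- **Low power comes from the sample size.** True: no choice of test or interval cures it. An interval does make the limitation visible.

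**Conclusion.** The point holds as a gap in the analysis plan. The outcome class used to justify 50 per arm has one stated comparison, a test with little ability to detect moderate increases in uncommon events, and no interval to show what remains possible. At the uncommon rates tried (1% v 4%, 2% v 4%, 5% v 10%), significance is reached in 5.4% to 14.5% of trials uncorrected and 0.6% to 6.3% by Fisher. At small counts the verdict can also depend on the unnamed version of the test. The power figures rest on assumed rates; the p-values for given tables and the 7.1% limit do not.

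Three stronger readings are not supported:

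- A reader might conclude that the trial misses harm about nine times in ten whatever the truth. That fits only small increases in uncommon events; at 10% v 30% the uncorrected test detects the difference in 73% of trials.
- A reader might conclude that a null result will be presented as safety. The protocol nowhere says so. It could be misread that way, which is reason enough to exclude it in writing.
- A reader might count complications as part of the reason for 50 per arm. The protocol names only side effects there; complications come in because the same chi-square rule covers them.

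**What to change.** In Statistical Analysis, replace the chi-square rule for secondary outcomes 7–9 with the following:

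1. As the main safety summary, report the number of women with each event per arm with an exact 95% interval, and the risk difference with a score-type 95% interval (Newcombe or Miettinen–Nurminen).
2. If a p-value is kept, name one exact test in advance, with its two-sided convention.
3. State that p≥0.05 could be misread and will not be reported as evidence of safety, and that 0/50 events in an arm still allows a true rate up to 7.1%.

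This needs no extra patients or visits. The cost is slightly more analysis work and a less favourable safety statement. It does not raise power for rare harms.

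### Three unranked primary outcomes share one unadjusted p<0.05 rule and nothing says which decides the trial; if any one counts, the false-positive rate is about 7% to 14%, not 5%.

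*Combined protocol and SAP*

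**What the plan says.** Under the heading Primary Outcomes measured, the protocol lists three items without ranking them:

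- The first is a directly measured volume, worded as "Estimated blood loss at time of procedure completion; using volume of cannister and weight of lap sponges".
- The second is derived from blood tests, and the protocol describes it as "Calculated Blood loss, using pre-operative hematocrit, postoperative hematocrit and estimated blood volume x Body Mass Index".
- The third concerns transfusion, and the protocol defines it as "Number of blood products received during admission that is directly due to blood loss at time of procedure".

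Statistical Analysis assigns t-tests to continuous variables and chi-square tests to categorical ones, and then states the only decision rule in the document: "P-values of less than 0.05 will be considered significant". It does not say which of the two tests a count of blood products receives.

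Two other places might be expected to identify the lead outcome:

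- **Specific aim.** Aim 1 begins "To compare the volume of blood loss in patients undergoing minimal invasive myomectomies" and does not say which measure of volume is meant. Aim 2 begins "To compare the number of blood products received during/post procedure", so transfusion is an aim in its own right.
- **Sample size.** The calculation is introduced with "Sample size calculation was set at 90 % power to detect a 150 ml difference in blood loss". Two of the three primary outcomes measure blood loss, and no power is given for blood products.

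The same paragraph states a one-sided alpha of 0.05 but puts 1.96, the two-sided 5% value, into the formula.

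**The concern.** With three primary outcomes and one threshold, the plan has to say what pattern of results makes the trial positive, and it does not. Requiring all three to be significant would keep the error rate at or below 5%. Counting any one would not. Because no rule is written, a report claiming success on one outcome out of three would not contradict the plan.

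This could easily matter here. One blood-loss measure comes from canister volume and sponge weight, the other from the change in hematocrit, so they can disagree. If they do, nothing fixed in advance says which stands, and the favourable one could be presented as the result. The 5% level quoted beside it would not be the error rate of the trial's main conclusion.

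**Working it through.** **Inputs from the documents.** Three primary outcomes; threshold 0.05 for each; SD 135 mL; difference 150 mL; z-values 1.96 and 1.282; 17 per group calculated, 50 per arm planned.

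**Assumed, because the documents give no figure.** The correlations between the test statistics; transfusion rates; SDs other than 135 mL; and a chi-square test on any transfusion (yes/no) standing in for the count of products.

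**1. The plan's own figure.** N = 2 × 135² × (1.96 + 1.282)² / 150² = 36,450 × 10.511 / 22,500 = 17.03, which matches the stated 17. With the one-sided value, 1.645, the formula gives 13.9. The calculation is therefore two-sided at 5% in effect, whatever the text says.

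**2. Any one of three two-sided 5% tests.** Independent: 1 − 0.95³ = 0.1426. Upper bound under any dependence, if each test holds its level: 3 × 0.05 = 0.15. For k normal test statistics with common correlation ρ, the rate is

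1 − ∫ [Φ((1.96 − √ρ·u)/√(1−ρ)) − Φ((−1.96 − √ρ·u)/√(1−ρ))]^k φ(u) du.

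| ρ | Three tests | Two blood-loss tests only |
|---|---|---|
| 0 | 14.3% | 9.8% |
| 0.3 | 13.6% | 9.5% |
| 0.5 | 12.5% | 9.1% |
| 0.8 | 9.8% | 7.8% |
| 0.9 | 8.4% | 7.0% |
| 0.95 | 7.3% | 6.5% |

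The right-hand column applies if blood products never reach significance, or if the sample-size paragraph is read as making blood loss the only primary concept.

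**3. Rare transfusion.** At an assumed 2% per arm with 50 per arm, the exact size of the uncorrected chi-square test on any transfusion is 1.3%. Under independence the overall rate is 1 − 0.95² × 0.987 = 10.9%. Simulating two t-tests and one chi-square test, with assumed transfusion rates from 2% to 20% and a range of correlations, gave 7.7% to 14.1%.

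**4. False claims of benefit only.** Each two-sided test spends 2.5% on this side. Three tests: 1 − 0.975³ = 7.3% if independent, 4.2% at ρ = 0.9. Two tests: 1 − 0.975² = 4.9% and 3.5%.

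**5. If each test is one-sided at 0.05.** Three tests: 14.3% if independent, 8.0% at ρ = 0.9.

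**6. What adjustment costs.** Two-sample t-test, 50 per arm, difference 150 mL. The noncentrality is 150 / (SD × √(2/50)), which is 5.56 at SD 135.

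| SD (mL) | Power at 0.05 | Power at 0.05/3 |
|---|---|---|
| 135 (plan) | 99.98% | 99.9% |
| 200 (assumed) | 96% | 90% |
| 250 (assumed) | 84% | 71% |

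At SD 135, the difference detectable with 90% power moves from 88 mL to 101 mL.

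**The case against.** The strongest reply has four parts.

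- **The plan nowhere says that one significant outcome suffices.** That is true, and every rate above is conditional on that reading. But it does not say otherwise either, and that gap is the defect.
- **The high end is unrealistic.** Two measures of the same bleeding, and the products given because of it, will be positively correlated. This stands: 14.3% is a limiting case, and roughly 8% to 13% is more plausible. The low end of the headline range also needs care. About 7% comes either from two tests at correlation 0.9 or from three at 0.95.
- **The stated purpose is to show a reduction in blood loss, so only false benefit matters.** On that count, with rare transfusion, the rate is 4.9% to 3.5%, below 5%. The arithmetic is right, but the comparison should be with the 2.5% that a two-sided 5% test allows on that side.
- **The aims and sample size already centre on blood loss, and power is ample, so this is only wording.** The fix is indeed wording. But neither place chooses between the two blood-loss measures, and ample power at SD 135 mL does not help when a true null is being tested.

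Two further cautions stand. The yes/no transfusion calculation is a stand-in for the specified count. The conflict over sidedness is a separate fault that does not change the conclusion.

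**Conclusion.** The concern holds. The plan has three primary outcomes, one unadjusted threshold and no rule for declaring success. Neither the aims nor the sample size supplies one.

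If any one significant outcome counts, the overall two-sided false-positive rate is about 7% to 14% rather than 5%. The range rests on assumed correlations from independence to about 0.9–0.95, and it includes the case where the transfusion test contributes nothing. The bound of 15% needs no correlation assumption, only that each test holds its 5% level. If the investigators intend all three to be significant, there is no inflation, but the plan would have to say so. The omission affects the trial's main conclusion and should be corrected before unblinding.

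**What to change.** Before unblinding, write one success rule and state that all tests are two-sided. Either of these would do:

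- **Option A: single primary with fixed order.** Name one blood-loss measure as the sole primary outcome at two-sided 0.05. Then test the other blood-loss measure, then number of blood products, each at 0.05, stopping at the first non-significant result.
- **Option B: three primaries with Holm.** Keep all three at an overall two-sided 0.05. The smallest p-value is compared with 0.05/3, the next with 0.05/2 and the last with 0.05, stopping at the first failure.

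Whichever is chosen:

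- Say which blood-loss measure the sample size refers to.
- Reconcile the Study Design statement, "Blood loss will be estimated by the surgeon performing the procedure", with the canister-and-sponge definition in the outcome list.
- Write calculated blood loss as an explicit formula; the current wording cannot be computed as it stands.
- Name the test for the count of blood products.

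**Cost.** Protocol wording only, with no extra patients. Option A loses no power on the chosen measure, but a significant result on a demoted outcome alone, including blood products (aim 2), could no longer be claimed as primary success. Option B costs almost nothing for blood loss at SD 135 mL and more if the SD is larger, as tabulated above. Its cost for blood products cannot be computed from the documents, which give no transfusion rate. As an illustration only, with an assumed 10% against 5% of patients transfused, exact chi-square power is about 14% at 0.05 and 6% at 0.05/3. Holm would, however, test blood products at the full 0.05 once both blood-loss outcomes had passed.
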